5.4.6. Criteria and Procedures for Dose Interruptions and Adjustments

Treatment with INCAGN01876 in combination with immune therapies may be delayed up to 4 weeks (ie, 28 days) to allow for resolution of toxicity. **If an interruption or discontinuation is necessary, all study treatments should be interrupted or discontinued.** Subjects may resume treatment if no medical condition or other circumstance exists that, in the opinion of the investigator, would make the subject unsuitable for further participation in the study. The treating investigator should contact the medical monitor to discuss the case of any subject whose treatment has been delayed for more than 4 weeks (ie, 28 days) before restarting treatment.

Instructions for dose interruptions and modifications for INCAGN01876 are outlined in [Table 7](#). Doses of epacadostat may be modified according to the guidelines and dose levels described in [Table 6](#). Individual decisions regarding dose interruptions and modifications of INCAGN01876 and epacadostat should be made using clinical judgment in consultation with the medical monitor (whenever possible), taking into account relatedness of the AE to the study treatment and the subject's underlying condition. Adverse events that have a clear alternative explanation,

or transient (≤ 72 hours) abnormal laboratory values without associated clinically significant signs or symptoms, may be exempt from dose-reduction rules.

Dose interruptions are permitted in the case of medical/surgical events or logistical reasons not related to study treatment (eg, elective surgery, unrelated medical events, subject vacation, and/or holidays). Subjects should be placed back on study treatment within 4 weeks (28 days) of the scheduled interruption, unless otherwise discussed with the medical monitor. The reason for interruption should be documented in the subject's source documentation.

Table 6: Dose Modifications for Epacadostat

Dose of Epacadostat	Dose Level -1	Dose Level -2 ^a
	First Reduction of Epacadostat	Second Reduction of Epacadostat
█████ BID	█████ BID	█████ BID

^a No more than 2 dose reductions are permitted for epacadostat.

Table 7: Criteria for Interruption and Restarting of Study Treatment

Toxicity	Hold Treatment for Grade	Agent	Timing for Restarting Treatment	Dose Level for Restarting Treatment	Treatment Discontinuation
Diarrhea/colitis	2-3	Pembrolizumab	Toxicity resolves to Grade 0-1.	N/A	Toxicity does not resolve within 12 weeks of last dose or inability to reduce corticosteroid to 10 mg or less of prednisone or equivalent per day within 12 weeks.
		INCAGN01876		Grade 2: N/A Grade 3: Reduce by 1 dose level.	
		Epacadostat		Related: Reduce by 1 dose level. Not Related: Same dose level.	
	4	Pembrolizumab	Permanently discontinue.	N/A	Permanently discontinue.
		INCAGN01876			
		Epacadostat			
AST, ALT, or increased bilirubin	2	Pembrolizumab	Toxicity resolves to Grade 0-1.	N/A	Toxicity does not resolve within 12 weeks of last dose.
		INCAGN01876		N/A	
		Epacadostat		Related: Reduce by 1 dose level. Not Related: Same dose level.	
	3-4	Pembrolizumab	Permanently discontinue (see exception below) ^a .	N/A	Permanently discontinue (see exception below) ^a .
		INCAGN01876			
		Epacadostat			
T1DM (if new onset) or hyperglycemia	T1DM or 3-4	Pembrolizumab	Hold pembrolizumab, INCAGN01876, and epacadostat for new onset T1DM or Grade 3-4 hyperglycemia associated with evidence of beta cell failure.	N/A	Resume study medications when subjects are clinically and metabolically stable.
		INCAGN01876		Grade 2: N/A Grade 3-4: Reduce by 1 dose level.	
		Epacadostat		Related: Reduce by 1 dose level. Not Related: Same dose level.	

Table 7: Criteria for Interruption and Restarting of Study Treatment (Continued)

Toxicity	Hold Treatment for Grade	Agent	Timing for Restarting Treatment	Dose Level for Restarting Treatment	Treatment Discontinuation
Hypophysitis	2-4	Pembrolizumab	Toxicity resolves to Grade 0-1. Therapy with pembrolizumab, INCAGN01876, and epacadostat can be continued while endocrine replacement therapy is instituted.	N/A	Toxicity does not resolve within 12 weeks of last dose or inability to reduce corticosteroid to 10 mg or less of prednisone or equivalent per day within 12 weeks.
		INCAGN01876		Grade 2: N/A Grade 3: Reduce by 1 dose level.	
		Epacadostat		Related: Reduce by 1 dose level. Not Related: Same dose level.	
Hyperthyroidism	3	Pembrolizumab	Toxicity resolves to Grade 0-1.	N/A	Toxicity does not resolve within 12 weeks of last dose or inability to reduce corticosteroid to 10 mg or less of prednisone or equivalent per day within 12 weeks.
		INCAGN01876		Reduce by 1 dose level.	
		Epacadostat		Related: Reduce by 1 dose level. Not Related: Same dose level.	
	4	Pembrolizumab	Permanently discontinue.	N/A	Permanently discontinue.
		INCAGN01876			
		Epacadostat			
Hypothyroidism	N/A	Pembrolizumab	Therapy with pembrolizumab, INCAGN01876, and epacadostat can be continued while thyroid replacement therapy is instituted.	N/A	Therapy with pembrolizumab and epacadostat can be continued while thyroid replacement therapy is instituted.
		INCAGN01876			
		Epacadostat			
Infusion reaction	2	Pembrolizumab ^b	Toxicity resolves to Grade 0-1.	N/A	N/A
		INCAGN01876 ^b		Same dose level.	N/A
		Epacadostat		Same dose level.	N/A
	3-4	Pembrolizumab	Permanently discontinue.	N/A	Permanently discontinue.
		INCAGN01876			
		Epacadostat			

Table 7: Criteria for Interruption and Restarting of Study Treatment (Continued)

Toxicity	Hold Treatment for Grade	Agent	Timing for Restarting Treatment	Dose Level for Restarting Treatment	Treatment Discontinuation	
Pneumonitis	2	Pembrolizumab	Toxicity resolves to Grade 0-1.	N/A	Toxicity does not resolve within 12 weeks of last dose or inability to reduce corticosteroid to 10 mg or less of prednisone or equivalent per day within 12 weeks.	
		INCAGN01876		Reduce by 1 dose level		
		Epacadostat		Related: Reduce by 1 dose level. Not Related: Same dose level.		
	3-4 (or recurrent Grade 2)	Pembrolizumab	Permanently discontinue.	N/A		Permanently discontinue.
		INCAGN01876				
		Epacadostat				
Renal failure or nephritis	2	Pembrolizumab	Toxicity resolves to Grade 0-1.	N/A	Toxicity does not resolve within 12 weeks of last dose or inability to reduce corticosteroid to 10 mg or less of prednisone or equivalent per day within 12 weeks.	
		INCAGN01876		N/A		
		Epacadostat		Related: Reduce by 1 dose level. Not Related: Same dose level.		
	3-4	Pembrolizumab	Permanently discontinue.	N/A		Permanently discontinue.
		INCAGN01876				
		Epacadostat				
Rash	3 ^c	Pembrolizumab	Toxicity resolves to Grade 0-1.	Same dose level.	Toxicity does not resolve within 12 weeks of last dose or inability to reduce corticosteroid to 10 mg or less of prednisone or equivalent per day within 12 weeks.	
		INCAGN01876		Reduce by 1 dose level.		
		Epacadostat		Related: Reduce by 1 dose level. Not Related: Same dose level.		
	4	Pembrolizumab	Permanently discontinue.	N/A		Permanently discontinue.
		INCAGN01876				
		Epacadostat				

Table 7: Criteria for Interruption and Restarting of Study Treatment (Continued)

Toxicity	Hold Treatment for Grade	Agent	Timing for Restarting Treatment	Dose Level for Restarting Treatment	Treatment Discontinuation
All other drug-related toxicity	3 or Severe ^d	Pembrolizumab	Toxicity resolves to Grade 0-1.	N/A	Toxicity does not resolve within 12 weeks of last dose or inability to reduce corticosteroid to 10 mg or less of prednisone or equivalent per day within 12 weeks.
		INCAGN01876		Reduce by 1 dose level	
		Epacadostat		Related: Reduce by 1 dose level. Not Related: Same dose level.	
	4	Pembrolizumab	Permanently discontinue.	N/A	Permanently discontinue.
		INCAGN01876			
		Epacadostat			

^a For subjects with liver metastasis who begin treatment with Grade 2 AST or ALT, if AST or ALT increases by greater than or equal to 50% relative to baseline and lasts for at least 1 week, then subjects should be discontinued. The dose of INCAGN01876 and epacadostat should also be reduced by 1 dose level for subjects with liver metastasis that have Grades 3 to 4 AST or ALT elevations.

^b If symptoms resolve within 1 hour of stopping drug infusion, the infusion may be restarted at 50% of the original infusion rate (eg, from 100 mL/h to 50 mL/h). Otherwise, dosing will be held until symptoms resolve, and the subject should be premedicated for the next scheduled dose; see [Table 9](#) for further management details.

^c Subjects with Grade 3 rash in the absence of desquamation, with no mucosal involvement, that does not require systemic steroids, and that resolves to Grade 1 within 14 days do not have to hold study treatment.

^d Subjects with intolerable or persistent Grade 2 treatment-related toxicities may hold study treatment at the discretion of the investigator.

5.4.7. Management of Immune-Related Adverse Events

INCAGN01876, pembrolizumab, and epacadostat are considered immune modulators, and it is possible that irAEs (both nonserious and serious) may occur. Adverse events of a potential immunologic etiology, or irAEs, may be defined as AEs consistent with an immune phenomenon associated with drug exposure *after all other etiologies have been eliminated*. Immune-related AEs may be expected based on the nature of the study treatment, their mechanisms of action, and reported experience with these and other immunotherapies. Special attention should be paid to AEs that may be suggestive of potential irAEs. An irAE can occur shortly after the first dose or several months after the last dose of treatment. Suspected irAEs should be discussed with the medical monitor when possible.

Subjects should receive appropriate supportive care measures as deemed necessary by the treating investigator. Suggested supportive care measures for the management of treatment-related AEs with potential immunologic etiology are outlined in [Table 8](#). Detailed supportive care guidelines for specific irAEs can be found in [Appendix B](#). Pembrolizumab is an approved agent and has specific irAE management guidelines within the prescribing information; the treating investigator may use labeled guidance or institutional guidelines for the management of irAEs if preferred. For each AE, attempts should be made to rule out other causes, including, but not limited to, metastatic disease or bacterial or viral infection, which may require specific supportive care.

Table 8: Supportive Care Guidelines for Immune-Related Adverse Events

CTCAE Grade/Severity	Supportive Care ^a
Grade 1 (mild)	
 • Monitor symptoms and provide symptomatic treatment.
Grade 2 (moderate)	
 • Monitor symptoms and provide symptomatic treatment. • Consider consultation with specialists as necessary. • Consider systemic corticosteroids per institutional standard of care.
Grade 3-4 (severe to life-threatening)	
 • Monitor symptoms and provide symptomatic treatment. • Consider consultation with specialists as necessary. • Administer corticosteroids per institutional standard of care. • More potent immunosuppressive therapies should be considered for events not responding to systemic steroids after discussion with the medical monitor. • Study treatment may be permanently discontinued for clinically significant or severe irAEs or for events where the steroid course cannot be tapered below 7.5 mg/day prednisone or equivalent to manage symptoms.

^a Detailed supportive care guidelines for specific irAEs can be found in [Appendix B](#).

5.4.8. Management of Infusion Reactions

[Table 9](#) shows treatment guidelines for subjects who experience an infusion reaction associated with administration of study treatment. Signs and symptoms usually develop during or shortly after drug infusion and generally resolve completely within 24 hours of completion of the infusion. Pembrolizumab is an approved agent and has specific infusion reaction management guidelines within the prescribing information; the treating investigator may use labeled guidance or institutional guidelines for the management of infusion reactions if preferred.

Table 9: Infusion Reaction Treatment Guidelines for Pembrolizumab and INCAGN01876

CTCAE Grade	Treatment	Premedication at Subsequent Dose Administration
Grade 1: Mild reaction; infusion interruption not indicated; intervention not indicated.	Increase monitoring of vital signs as clinically indicated until the subject is deemed medically stable in the opinion of the investigator.	None.
Grade 2: Requires infusion interruption but responds promptly to symptomatic treatment (eg, antihistamines, NSAIDs, narcotics, IV fluids); prophylactic medications indicated for ≤ 24 hours.	
Stop infusion and monitor symptoms.
 
Additional appropriate medical therapy may include, but is not limited to, the following:
 
 • IV fluids • Antihistamines • NSAIDs • Acetaminophen • Narcotics 
Increase monitoring of vital signs as clinically indicated until the subject is deemed medically stable in the opinion of the investigator.
 
If symptoms resolve within 1 hour of stopping drug infusion, the infusion may be restarted at 50% of the original infusion rate. Otherwise, dose administration will be held until symptoms resolve, and the subject should be premedicated for the next scheduled dose.
 
Subjects who develop Grade 2 toxicity despite adequate premedication should be permanently discontinued from further study treatment.
	
Subject may be premedicated 1.5 h (± 30 min) before infusion with the following:
 
 • Diphenhydramine 50 mg orally (or equivalent dose of antihistamine). • Acetaminophen 500-1000 mg orally (or equivalent dose of antipyretic).
Grade 3: Prolonged (ie, not rapidly responsive to symptomatic medication and/or brief interruption of infusion); recurrence of symptoms following initial improvement; hospitalization indicated for other clinical sequelae (eg, renal impairment, pulmonary infiltrates).	
Stop infusion.
 
Additional appropriate medical therapy may include, but is not limited to, the following:
 
 • IV fluids • Antihistamines • NSAIDs • Acetaminophen • Narcotics • Oxygen 	No subsequent dose.
Grade 4: Life-threatening; pressor or ventilatory support indicated.	
 • Pressors • Corticosteroids • Epinephrine 
Increase monitoring of vital signs as clinically indicated until the subject is deemed medically stable in the opinion of the investigator.
 
Hospitalization may be indicated.
 
Subject is permanently discontinued from further study treatment.
	

Note: Appropriate resuscitation equipment should be available in the room, and a physician should be readily available during the period of study treatment administration.

5.4.9. Procedure for Subjects Exhibiting Serotonin Syndrome

As noted in [Section 1.3](#), there is a chance that epacadostat could cause an increase in serotonin levels in the brain that might trigger SS ([Boyer and Shannon 2005](#)) when administered in combination with other serotonergic agents. This syndrome has been most closely associated with use of MAOIs, meperidine, linezolid, or methylene blue; all of these agents are prohibited during the study. Selective serotonin reuptake inhibitors and SNRIs are permitted in the study. The following procedures will be implemented if subjects exhibit the signs/symptoms of SS described in [Table 10](#), including tremor; hyperreflexia; and spontaneous, ocular, or inducible clonus, together with agitation, fever, diaphoresis, or muscle rigidity:

- Immediately interrupt epacadostat, pembrolizumab, and INCAGN01876 administration.
- Immediately interrupt any SSRI or SNRI administration.
- Provide appropriate medical management of the subject until all signs/symptoms are resolved (eg, IV fluids and/or sympathomimetic amines for hypotension, benzodiazepines for agitation, administration of 5-hydroxytryptamine antagonists, such as cyproheptadine).
- If subject chooses to remain in the study, restart treatment with all study medications after the SSRI or SNRI has been discontinued and no sooner than when 5 half-lives have elapsed for the specific SSRI or SNRI in question and after resolution of signs/symptoms of SS. The SSRI or SNRI treatment MAY NOT be restarted.
- If subject chooses to withdraw from the study or must restart treatment with SSRI or SNRI, the subject should be scheduled for a follow-up visit (see [Section 6.4](#)). Treatment with SSRI or SNRI may be initiated 2 weeks after resolution of signs and symptoms of SS.

Table 10: Signs and Symptoms of Serotonin Syndrome

Tremor and hyperreflexia
Spontaneous clonus
Muscle rigidity, temperature > 38°C (100.4°F), and either ocular clonus or inducible clonus
Ocular clonus and either agitation or diaphoresis
Inducible clonus and either agitation or diaphoresis

5.4.10. Criteria for Permanent Discontinuation of Study Treatment

The occurrence of unacceptable toxicity not caused by the underlying malignancy will be presumed to be related to study treatment and will require that the study treatment be permanently discontinued. Unacceptable toxicity is defined as follows:

- Grade 4 or life-threatening AEs, except with approval from the medical monitor.
- Toxicity requiring more than 2 dose reductions of INCAGN01876 (see [Table 1](#)) or epacadostat (see [Table 6](#)).
- ≥ Grade 2 ocular irAE.

- Occurrence of an AE that is related to treatment, in the judgment of the investigator or the medical monitor, and compromises the subject's ability to continue study-specific procedures or is considered to not be in the subject's best interest.
- Persistent AE requiring a delay of treatment for more than 4 weeks (ie, 28 days), unless a greater delay has been approved by the sponsor.

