Note: Bisphosphonates and denosumab are permitted concomitant medications.
 - b. ≤ 28 days for prior immune therapy or persistence of active cellular therapy (ie, chimeric antigen receptor T-cell therapy; other cellular therapies must be discussed with the medical monitor to determine eligibility).
 - c. ≤ 28 days for a prior mAb used for anticancer therapy, with the exception of denosumab.
 - d. ≤ 7 days for immune-suppressive-based treatment for any reason.
Note: Use of inhaled or topical steroids or corticosteroid use for radiographic procedures is permitted.
Note: Must not require chronic use of corticosteroids. The use of physiologic corticosteroid replacement therapy may be approved after consultation with the medical monitor.
 - e. ≤ 28 days or 5 half-lives (whichever is longer) before the first dose for all other investigational agents or devices. For investigational agents with long half-lives (eg, > 5 days), enrollment before the fifth half-life requires medical monitor approval.
5. Has not recovered to \leq Grade 1 from toxic effects of prior therapy (including prior immune therapy) and/or complications from prior surgical intervention before starting therapy.
Note: Subjects with stable chronic conditions (\leq Grade 2) that are not expected to resolve (such as neuropathy and alopecia) are exceptions and may enroll.
Note: Subjects with a history of any grade immune-related ocular AE (eg, episcleritis, scleritis, uveitis) will be excluded.
Note: Subjects with a history of a Grade 3 or higher immune-related AE from prior immunotherapies are excluded from the dose-escalation portion of the study.
6. Receipt of a live vaccine within 30 days of planned start of study treatment.
Note: Examples of live vaccines include, but are not limited to, the following: measles, mumps, rubella, chicken pox/zoster, yellow fever, rabies, Bacillus Calmette-Guérin, and typhoid vaccines. Seasonal influenza vaccines for injection are generally killed virus vaccines and are allowed; however, intranasal influenza vaccines (eg, FluMist[®]) are live attenuated vaccines and are not allowed.
7. Current use of prohibited medication as described in [Section 5.6.3](#).

8. Active autoimmune disease that required systemic treatment in the past (ie, use of disease-modifying agents, corticosteroids, or immunosuppressive drugs).
Note: Subjects who have not required systemic treatment in the past 2 years should discuss their case with the medical monitor to determine eligibility.

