5.5. Withdrawal of Subjects From Study Treatment

5.5.1. Withdrawal Criteria

A subject may choose to withdraw from the study treatment at any time or be withdrawn from the study treatment by the investigator or sponsor if the subject is noncompliant with the study requirements. If a subject is withdrawn from study treatment, then every reasonable effort should be made to determine the reason for withdrawal, and this information should be recorded in the eCRF.

Subjects **must** be withdrawn from **study treatment** for the following reasons:

- The subject becomes pregnant.
- Consent is withdrawn. Subjects may choose to withdraw from the study at any time without penalty of jeopardizing their healthcare or loss of benefits to which the subject is otherwise entitled.
Note: Consent withdrawn means that the subject can no longer be followed and no additional data can be collected. Subjects may choose to discontinue study treatment and remain in the study to be followed for progression and survival.
- Further participation would be injurious to the subject's health or well-being, in the investigator's medical judgment.
- Unacceptable toxicity (see [Section 5.4](#)) occurs. Subjects with unacceptable toxicities must be withdrawn from study treatment but will continue in the follow-up phase of the study (see [Section 6.4](#)).
- The study is terminated by the sponsor.
- The study is terminated by the local health authority, IRB, or IEC.

A subject **may** be discontinued from **study treatment** as follows:

- Confirmed radiographic progression of disease per RECIST v1.1. A subject may be granted an exception to continue on treatment with confirmed radiographic progression if clinically stable or clinically improved (see [Section 7.7.1](#)).
Note: For unconfirmed progression, see [Section 7.7.1](#).
- If, during the course of the study, a subject is found not to have met eligibility criteria (see [Section 3](#)), the medical monitor, in collaboration with the investigator, will determine whether the subject should be withdrawn from study treatment.
- If a subject is lost to follow-up or noncompliant with study procedures or study treatment in the investigator's opinion, the sponsor should be consulted for instruction on handling the subject.

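### Table 7 has no ocular irAE row, so its catch-all row contradicts the mandatory stop at Grade 2 or higher in Protocol 5.4.10; three Grade 4 provisions also omit the approval step

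*Protocol*

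**What the plan says.** **The stop rule.** Protocol Section 5.4.10 defines unacceptable toxicity and requires permanent discontinuation when it occurs. Two of its criteria matter here. The first is "≥ Grade 2 ocular irAE", with no exception attached. The second is "Grade 4 or life-threatening AEs, except with approval from the medical monitor". Section 5.5.1 then gives the consequence: "Subjects with unacceptable toxicities must be withdrawn from study treatment".

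**The dosing table.** Section 5.4.6 directs sites to Table 7 for interrupting and modifying INCAGN01876. The table sets out, by toxicity and grade, when to hold, when to restart, at what dose, and when to stop. It names 10 toxicities and closes with a catch-all row for other drug-related toxicity. In that row a Grade 3 or severe event is held until Grade 0-1 and INCAGN01876 is restarted one dose level lower; Grade 4 is a permanent stop. Footnote d to that row adds: "Subjects with intolerable or persistent Grade 2 treatment-related toxicities may hold study treatment at the discretion of the investigator".

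**Grade 4 in Table 7.** For T1DM or Grade 3-4 hyperglycemia the discontinuation column reads "Resume study medications when subjects are clinically and metabolically stable". For hypophysitis Grade 2-4 the table allows restart at Grade 0-1 and adds "Therapy with pembrolizumab, INCAGN01876, and epacadostat can be continued while endocrine replacement therapy is instituted". Footnote a prescribes a reduction of one dose level in INCAGN01876 and epacadostat for subjects with liver metastasis and Grade 3-4 AST or ALT.

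**Ocular events elsewhere.** Section 3.2 states: "Subjects with a history of any grade immune-related ocular AE (eg, episcleritis, scleritis, uveitis) will be excluded". Table 5 makes an ocular irAE of Grade 2 or higher a dose-limiting toxicity.

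**The concern.** Table 7 is the page a site opens when deciding whether to give the next dose. It has its own discontinuation column and prescribes permanent stops for many events, so a reader would expect every toxicity-specific stop to appear there. The ocular stop does not. Nor does Appendix B, the other guide arranged by toxicity, have an ocular entry. The protocol plainly regards ocular events as special, since a history of any grade excludes a patient and Grade 2 is dose-limiting.

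At stake is a patient with, say, Grade 2 or 3 uveitis who is kept on treatment or re-dosed because the site followed the table, when the protocol says that treatment must end. A lesser worry is further dosing after a Grade 4 endocrine or liver event without the approval that 5.4.10 demands.

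**Working it through.** No sample size, error rate or other statistic is involved. The check sets Table 7 beside Sections 5.4.10 and 5.5.1 and counts entries.

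**Step 1: where an ocular irAE falls.** The named toxicities in Table 7 are diarrhea/colitis, AST/ALT/bilirubin, T1DM/hyperglycemia, hypophysitis, hyperthyroidism, hypothyroidism, infusion reaction, pneumonitis, renal failure/nephritis and rash. That is 10, of which 0 are ocular. Section 5.4.7 describes an irAE as associated with drug exposure once other causes are ruled out, so the event belongs in the catch-all row.

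**Step 2: the two instructions by grade.**

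| Ocular irAE | 5.4.10 with 5.5.1 | Table 7 catch-all row | Agree? |
|---|---|---|---|
| Grade 2 | Permanent stop | At most an optional hold (footnote d) | No |
| Grade 3 | Permanent stop | Hold; restart at Grade 0-1, INCAGN01876 one level lower | No |
| Grade 4 | Permanent stop | Permanent stop | Yes |

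At Grade 2 the table permits what 5.4.10 forbids, and at Grade 3 it lays out a restart that 5.4.10 forbids. The ocular criterion has no approval route, so the two cannot be reconciled by asking the medical monitor.

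**Step 3: Table 7 entries that name Grade 4.**

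- Permanent stop, no exception (7): diarrhea/colitis 4, hyperthyroidism 4, infusion reaction 3-4, pneumonitis 3-4, renal 3-4, rash 4, all other 4.
- Permanent stop with the footnote a exception (1): AST/ALT/bilirubin 3-4.
- Further dosing allowed (2): T1DM/hyperglycemia 3-4, hypophysitis 2-4.

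Total 7 + 1 + 2 = 10. Provisions that give terms for further dosing without naming approval: 2 rows + 1 footnote = 3.

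**Step 4: how explicit each of the three is.**

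- T1DM/hyperglycemia is the clearest: it states an INCAGN01876 reduction of one level for Grade 3-4 and then resumption.
- Hypophysitis covers Grades 2-4 in its hold and timing cells, but its INCAGN01876 dose cell addresses only Grades 2 and 3. No Grade 4 dose is given.
- Footnote a names Grades 3 to 4 and a dose reduction.

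**Step 5: can both texts be followed at Grade 4?** Yes. Section 5.4.10 allows further dosing with approval, and Table 7 supplies timing and, where stated, dose. A site that obtains approval and then applies the table meets both. The fault is that the table does not repeat the condition.

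**The case against.** The best reply is that the specific rule governs the general one. Section 5.4.10 names ocular irAE in categorical terms, Section 5.5.1 says must, and Table 7 offers only a generic row with a permissive footnote. Harm requires a site to read the table and overlook both sections.

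Much of this stands. A reader might infer that the protocol leaves precedence open, because 5.5.1 points only to Section 5.4 as a whole and that section contains Table 7 too. The documents do not support that reading: 5.5.1 attaches the reference to unacceptable toxicity, a term defined only in 5.4.10, so 5.4.10 binds. This settles which rule is right. It does not remove the opposite instruction from the table that sites are sent to for dosing decisions.

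On Grade 4, a reader might infer that Table 7 contradicts 5.4.10. It does not, as Step 5 shows. The medical monitor is also not absent: Section 5.4.6 asks for consultation where possible, and the Grade 3 or 4 endocrinopathy guidance in Appendix B, which covers hypophysitis, says to consult the monitor. Consultation is still weaker than the approval that 5.4.10 names, so the omission remains.

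A reader might also add hypothyroidism as a fourth Grade 4 provision, since its row allows treatment to continue and Appendix B permits this at Grade 3 or 4 without interruption. The row's hold grade is marked not applicable and names no grade, and Appendix B is supportive-care guidance outside Table 7. It should not be counted.

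**Conclusion.** The ocular point holds in full for Grades 2 and 3: Table 7 gives an optional hold or a restart where 5.4.10 and 5.5.1 require a permanent stop. The Grade 4 point holds only as an omission, in three provisions: T1DM/hyperglycemia, hypophysitis and footnote a.

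Severity is minor. This is a safety instruction to sites and affects no endpoint, sample size or analysis. The practical risk assumes a site that doses from Table 7 alone. One should not infer that any patient was wrongly re-dosed, because the documents show no such subject. SAP Section 10.1.1.2 reports that screening and enrollment stopped with a limited number of subjects in Treatment Group C and none in Groups B and D. That limits the exposure but does not by itself remove it: treatment may run for up to 24 months, and the documents do not say whether anyone remained on treatment.

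**What to change.** Make three edits to Table 7:

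1. Add a row: *Ocular irAE, Grade 2 or higher: permanently discontinue all study treatment.*
2. Add *Grade 4: only with medical monitor approval* to the T1DM/hyperglycemia entry, the hypophysitis entry and footnote a.
3. Add a line stating that Section 5.4.10 prevails over the table.

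The cost is one row, one short phrase used three times and one sentence, made by amendment with a letter to sites. It needs no extra visits, staff or patients, and it states the sponsor's existing stop rule where sites will look for it.
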